CLIA	Clinical Laboratory Improvement Amendments
CMP	Clinical Monitoring Plan
CMS	Centers for Medicare and Medicaid Services
CRF	Case Report Form
CRO	Contract Research Organization
DCC	Data Coordinating Center
DHHS	Department of Health and Human Services
DSMB	Data Safety Monitoring Board
eCRF	Electronic Case Report Forms
FDA	Food and Drug Administration
FFR	Federal Financial Report
GCP	Good Clinical Practice
IB	Investigator's rochure
ICH	International Conference on Harmonisation
IND	Investigational New Drug Application
IRB	Investigational Review Board
MedDRA	Medical Dictionary for Regulatory Activities
MOP	Manual of Procedures
OHRP	Office for Human Research Protections
PI	Principal Investigator
QA	Quality Assurance
QC	Quality Control
SAE	Serious Adverse Event
SAP	Statistical Analysis Plan
SMC	Safety Monitoring Committee
SOC	System Organ Class
SOP	Standard Operating Procedure
US	United States

STATEMENT OF COMPLIANCE

The trial will be carried out in accordance with Good Clinical Practice (GCP) as required by the following (use applicable regulations depending on study location and sponsor requirements; examples follow):

- United States (US) Code of Federal Regulations (CFR) applicable to clinical studies (45 CFR Part 46, 21 CFR Part 50, 21 CFR Part 56, 21 CFR Part 312, and/or 21 CFR Part 812)
- ICH E6

All key personnel (all individuals responsible for the design and conduct of this trial) have completed Human Subjects Protection Training.

I agree to ensure that all staff members involved in the conduct of this study are informed about their obligations in meeting the above commitments.

Principal Investigator: _____

Signed: _____ Date: _____

PROTOCOL SUMMARY

Title	Phase I Clinical Trial of Evaluating [⁶⁸ Ga] Ga-NOTA-SNA002 for the Safety Tolerance, Radiation Absorbed Dose and Dosimetry in Patients With Solid Tumor.
Proposed Indication	[⁶⁸ Ga] Ga-NOTA-SNA002, as a radiodiagnostic drug, is suitable for detecting PD-L1 positive lesions in solid tumor patients in combination with PET imaging.
Clinical Trial Phase	Phase 1
Study Drugs	SNA002 is a diagnostic recombinant [⁶⁸ Ga]-NOTA-PD-L1 single domain antibody (M18B) injection for intravenous use.
Sponsor	SmartNuclide Biopharma Co., Ltd.
Objective	To determine the safety, pharmacokinetics (PK), biodistribution, dosimetry, and tumor targeting potential of SNA002.
Study Population	Patient 18-75 years of age, male or female, with solid tumors
Number of Patients Planned	The study plans to recruit approximately 12-28 patients. The actual sample size will be dependent upon meeting the dose escalation criteria.
Objectives	
Primary objectives
 
To evaluate the safety and tolerability of single doses of SNA002 administered intravenously in patients with solid tumors
 
To assess the biodistribution of SNA002 in patients with solid tumors
 
Secondary objectives
 
To assess the radiation dosimetry of SNA002 in patients with solid tumors
 
To assess the radiation dose of SNA002 in the blood of patients with solid tumors
 
To assess the PET imaging characteristics of SNA002 in patients with solid tumor
 
To identify the optimal dose
 
To identify optimal image timing window
 
Exploratory objectives
 
To explore the correlation between the PET imaging characteristics of SNA002 and PD-L1 binding and the histological PD-L1 expression patterns.
 
To explore the positive and negative predictive efficacy of [⁶⁸Ga] Ga-NOTA-SNA002.

Endpoint	
Primary Endpoints
 
Incidence of treatment-emergent adverse events (TEAEs) and serious adverse events (SAEs)
 
Dosimetry and biodistribution
 
Secondary Endpoints
 
Radiation dosimetry of SNA002
 
Radiation exposure: detecting radioactivity in the blood
 
Recommended diagnostic dose of SNA002
 
Optimal imaging window
 
SUV_{max} (Standardized uptake value), SUV_{mean}, tumor to background ratio, and tumor to blood ratio.
 
PK parameters of SNA002: Including but not limited to maximum serum concentration (C_{max}), time to reach maximum serum concentration (T_{max}), and area under the serum concentration versus time curve from time zero to time (AUC_{0-τ}), and terminal half-life (T_{1/2}).
 
Immunogenicity: incidence of anti-drug antibodies

Study Design	
Overall Study Design
 
This is an open-label, dose escalation study to evaluate the safety, PK, biodistribution, dosimetry, and tumor targeting potential of SNA002 in patients with solid tumors.
 
This study will consist of Screening Period, Baseline Period, Study Period and Safety Follow-up Period. A signed and dated informed consent form will be obtained before any study-related procedures are performed. Collect CT/MRI/PET/CT results from subjects within one month before screening to obtain baseline tumor assessment. Eligible patients will be enrolled at least two days before the administration of study drug. The radiation dose for all dose groups at the time of administration should be ranged from 37 to 200MBq. Four dose levels of NOTA-SNA002 are planned: 0.1mg, 0.3mg, 0.5mg and 0.9mg. The final drug product administered to the patient is [⁶⁸Ga]Ga-NOTA-SNA002. Three to seven patients will be sequentially enrolled into each dose cohort. Patients will be administered a single dose of SNA002 over 1 minute as an intravenous bolus. Patients will be observed for 6±1h and 24±6h post infusion for infusion-related and other adverse reactions. In the first cohort of patients, whole body imaging will be acquired using PET/CT at 15±5 minutes, 60±10 minutes and 120±20 minutes post-injection. Before each imaging, the patients need to empty bladder as much as possible. Total-body PET-CT scans can be performed on 1-2 subjects in a certain dose group or each dose group, covering at least one of the aforementioned time points. In the subsequent cohorts,

	
the imaging schedule may be modified based on the imaging data from the first cohort of patients.
 
The optimal time point for PET scanning will be determined based on the analysis of the tumor to background ratio and tumor to blood pool ratio at different timepoints. Tumor to background ratio is defined as the ratio between tumor tracer uptake and the radioactivity on the opposite site or gluteus maximus, etc. The first PET scan will be performed in combination with a low-dose CT scan for attenuation correction and anatomic reference. An independent radiology review committee (IRC), consisting of principal investigator and nuclear medicine physicians, will be established to evaluate all imaging data.
 
If there is no radioactivity or a small amount of radioactivity in the target lesion as evaluated by the IRC, and the safety criteria are met, the dose will be escalated per the escalation guidelines. If the tumor to background ratio is high per the IRC, three patients will be enrolled at the next higher level and the IRC will determine whether dose escalation should stop based on the imaging data from these three patients. Blood samples will be collected from a peripheral vein to evaluate ADA, PK and the radioactivity in the circulation.
 
 • The time points for blood sample collection are as follows: within 30 minutes before injection of SNA002, at 2 ± 1 minutes, 5 ± 1 minutes, 10 ± 1 minutes, 30 ± 2 minutes, 50 ± 5 minutes, 100 ± 5 minutes and 150 ± 10 minutes post injection. All blood samples are sent to the central laboratory for PK analysis. Radioactivity in the blood sample (whole blood and serum) will be obtained using a γ-well-type detector and measured activity concentrations will be converted to percentage injected activity/L. • Urine sample will be collected to evaluate the renal excretion of radioactivity before injection, at 90 ± 30 minutes, 180 ± 30 minutes and 300 ± 30 minutes post injection. Counts in aliquots of serum or urine will be obtained using a γ-well-type detector and measured activity concentrations will be converted to percentage injected activity/L. 
Blood samples will be taken 30 minutes before administration, on $D6\pm 1$d and $D28\pm 2$d, and will be sent to the central laboratory for ADA analysis. Patients were discharged from the study after blood samples were collected on $D28\pm 2$d. Following the last PET scan, tumor biopsies or operation (if surgery is available) will be obtained. The investigator will determine the number and location of lesions for biopsy for each patient in consultation with the surgeon or interventional radiologist; these should be easily accessible and have positive or negative tracer uptake. Biopsy sites should not exceed 5 for each patient and ideally include both negative lesions and positive lesions. If taken an operation on tumor, the IRC will observe IHC result of tumor and PET scan.
 
The study will be end for patient after completing blood collection on $D28\pm 2$d.
 
Region-of-Interest Definition
 
Regions of interest (ROIs) will be used to determined SNA002 uptake in different organs. Organs with tracer uptake will be drawn using PMOD software based on the PET image, including all activities on the PET images that are contributing to the organ. For organs without tracer uptake, organ delineation will be based on CT data.
 
To calculate the biodistribution and dosimetry in normal organs with tracer uptake, a semiautomatic (region grow) method will be used to delineate the ROI on the PET images. For normal organs without tracer uptake, the ROI will be delineated based on CT scan.
 
Dosimetry
 
Time-activity curves were derived from volumes of interest for each source organ (i.e., brain, heart, lungs, liver, spleen, kidneys, and thyroid) delineated on the whole-body images using PMOD.
 
To define volumes of interest (VOIs) the dynamic study was loaded with all or some frames averaged, depending on the evaluated organ. VOIs were defined manually for heart, liver, gallbladder, kidneys with all frames averaged.
 
Using the PMOD software the VOIs consisted of regions of interest (ROIs) which were defined at the outer contour of the organ. In this way (decay-corrected) TACs of the organs' average radioactivity concentrations and their volumes were obtained.
 
An example, FYI: Source Organs: For dosimetric calculations, the following source organs were included: kidneys, red marrow, cortical bone mineral surface, trabecular bone mineral surface, urinary bladder content, and remainder body. Red marrow activity uptake was estimated from venous blood sampling.
				
	
  
 Dose Levels (mg)	Number of patients	
   
 0.1	3-7	
  
	Dose Levels (mg)	Number of patients	0.1	3-7
Dose Levels (mg)	Number of patients				
0.1	3-7				

	0.3	3-7	
	0.5	3-7	
	0.9	3-7	

Dose escalation criteria

Since SNA002 contains a PD-L1 nanobody that cannot block the binding of PD-1 to its ligands and the dose of PD-L1 antibody is extremely low, the main safety risk is likely to be occurrence of infusion-related reactions (IRRs), which are medically manageable. The dose escalation criteria will include image quality criteria and safety criteria (e.g., serious adverse events, Grade 2 or higher adverse events) as described below.

PD-L1 expression will be measured using immunohistochemistry [(IHC); 22C3-IHC assay] by obtaining at least one biopsy of a target lesion that is amenable to aspiration biopsy on Day 2. IHC results will be reviewed by the IRC. The correspondence between the IHC assay results and the PET imaging results will be evaluated by the IRC.

Dose-Escalation Rules

The dose escalation is determined through both imaging results and safety results:

- 1) **Imaging:** If the first three positive tumor lesions in a certain dose group judged by the IRC to having a high image quality (such as $T/B > 1.5$, etc.), it can be decided from the imaging perspective to increase to the next dose group after continuing to enroll 3-4 cases in this dose group, or directly increase to the next dose group for further exploration;
 - If the quality of the first 3 cases in the subsequent dose group is comparable to that in the previous dose group, the IRC shall discuss whether to discontinue further enrollment from a imaging perspective (e.g. The image quality of the first 3 cases in the 0.3mg dose group is similar to that in the 0.1mg dose group, then stop recruiting, and the 0.1mg dose was identified as the optimal image dose).
 - If the quality of the first 3 cases in the posterior dose group is higher than that in the prior, another 3 to 4 cases will be enrolled. After the completion of the posterior dose group, the IRC will discuss and decide whether this group should not be explored from the imaging aspect (e.g. The image quality of the first 3 cases in the 0.3mg dose group is higher than that in the 0.1mg dose group, then 3-4 cases continued to be enrolled in the 0.3mg dose group, and the subsequent dose exploration was not carried out, the 0.3mg dose was identified as the optimal image dose).
- 2) If the first three positive tumor lesions in a certain dose group judged by the IRC to present poor imaging quality (such as $T/B \leq 1$) or nonvisualization (functional imaging without nuclides), the decision of stopping enroll in this dose group can be made from an imaging perspective, and the dose group can directly increase to the next or second dose group (for example, if the imaging quality of the 0.1mg dose group is poor in three consecutive cases, the dose group can increase to the 0.3mg or 0.5mg dose group);
- 3) If the last dose group shows nonvisualization of the positive tumor lesions determined by the IRC in the first three cases, discussion will be conducted to determine whether to adjust the subsequent dose from the imaging perspective to explore or terminate the entire clinical trial.
- 4) After the dose escalation of all dose groups is completed, the imaging expert committee and the principal investigator will decide whether to continue enrolling 3-4 subjects in a certain initially identified optimal dose group for further exploration.

Security:

The principal investigator determines whether to increase the dose from the perspective of safety. Dose escalation should be stopped if one of the principles happen: ① If at least half of subjects in a dose group experience CTCAE grade 2 (or moderate) or above adverse reactions; ② or at least 1/3 subjects experience CTCAE grade 3 (or severe) or above adverse reactions; ③ or one serious adverse reaction in certain group.

The dose escalation will be determined by the principal investigator based on both imaging and safety results.

[figure not shown]
During the clinical trial, based on the principle of subject protection, the dose group can be rapidly escalated to the subsequent dose group if nonvisualization or the above safety events happens after only one subject is enrolled at the investigator's discretion.

Dose Selection Rationale

SNA002 does not bind to mouse, rat and dog PD-L1. Therefore, cynomolgus monkey was chosen in biodistribution studies and repeat-dose general toxicity studies. ^{68}Ga -NOTA-SNA002 can specifically bind to PD-L1 proteins of primates, and the radioactivity uptake is

	low in other organs except for the excretion organs (kidneys and bladder). The estimated absorbed dose (effective dose) converted from cynomolgus monkeys to adult male or female is 0.022-0.023mSv/MBq, which shows good radiation safety. The recommended dose of ^{68}Ga -NOTA-SNA002 for clinical trials is 185 MBq (5mCi), which generates an effective dose of about 4.1 mSv indicating safe use of ^{68}Ga -NOTA-SNA002 for clinical diagnostics. A NOAEL approach based on the pivotal monkey 2-week study toxicity findings was used to determine the maximum recommended starting dose (MRSD) for the first in human study. In the 2-week monkey study, the potential infusion reaction is the only toxicity observed after 3 repeated iv doses. the dose of 1.5 mg/kg (mean AUC $0\text{-}t$ = 20700 ng \cdot h /mL; mean C_{max} = 32000ng/mL) and 0.5mg/kg (mean AUC $0\text{-}t$ = 5060 ng \cdot h /mL; mean C_{max} = 10500ng/mL) was considered the NOAEL for males and females, respectively. Since the molecular weight of ^{68}Ga -NOTA-SNA002 is less than 100KD, The HED is 0.48 mg/kg (male) and 0.16 mg/kg (female) based on body surface. The MRSD is considered to be 0.048 mg/kg (male) and 0.016 mg/kg (female) (1/10 of NOAEL). The highest dose that nonclinical can cover is considered to be 0.24 mg/kg (male) and 0.08 mg/kg (female) (1/2 of NOAEL). The proposed human dose ranges are from 0.00167 mg/kg (0.1mg flat dose) starting dose to the highest ascending dose 0.01503mg/kg (0.9mg flat dose). The starting dose is 28.74- and 9.58-fold lower than the MRSD for males and females, respectively. The highest ascending 0.01503 mg/kg is covered by nonclinical data (1/2 of the NOAEL). Therefore, the proposed clinical mass dose range of 0.00167mg/kg to 0.01503mg/kg is not expected to pose a significant risk to patient safety.
Duration of Study Participation	Patients will be administered a single dose of SNA002. The duration of study participation will be approximately 42 days, including a screening period up to 14 days and a follow-up period up to 28 days (patients who experience AEs will be followed until resolution).

SCHEMATIC OF STUDY DESIGN

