6.1.7.2 Dose Escalation Schedule

The dose escalation is determined through both imaging results and safety results:

Imaging:

The Imaging Reviewer Committee consisted of the principal investigator and nuclear medicine physicians.

- 1) If the first three positive tumor lesions in a certain dose group judged by the IRC having a high image quality (such as $\text{T}/\text{B} > 1.5$, etc.), it can be decided from the imaging perspective to increase to the next dose group after continuing to enroll 3-4 cases in this dose group, or directly increase to the next dose group for further exploration;
→If the quality of the first 3 cases in the subsequent dose group is comparable to that in the previous dose group, the IRC shall discuss whether to discontinue further enrollment from a

imaging perspective (e.g. The image quality of the first 3 cases in the 0.3mg dose group is similar to that in the 0.1mg dose group, then stop recruiting, and the 0.1mg dose was identified as the optimal image dose).

- If the quality of the first 3 cases in the posterior dose group is higher than prior, another 3 to 4 cases will be enrolled. After the completion of the posterior dose group, the IRC will discuss and decide whether this group should not be explored from the imaging aspect (e.g. The image quality of the first 3 cases in the 0.3mg dose group is higher than that in the 0.1mg dose group, then 3-4 cases , and the subsequent dose exploration was not carried out, and the 0.3mg dose was identified as the optimal image dose).

- 2) If the first three positive tumor lesions in a certain dose group judged by IRC present poor imaging quality (such as $T/B \leq 1$) or nonvisualization (functional imaging without nuclides), the decision of stopping enroll in this dose group can be made from an imaging perspective, and the dose group can directly increase to the next or second dose group (for example, if the imaging quality of the 0.1mg dose group is poor in three consecutive cases, the dose group can increase to the 0.3mg or 0.5mg dose group);
- 3) If the last dose group shows nonvisualization of the positive tumor lesions determined by the IRC in the first three cases, discussion will be conducted to determine whether to adjust the subsequent dose from the imaging perspective or terminate the entire clinical trial.

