9. ADA: blood samples were collected within 30 minutes before administration, on D6 ± 1d and D28 ± 2d during the safe follow-up period. All blood samples were tested in an independent third-party central laboratory.
10. Systemic PET-CT: Three systemic PET CT scans are performed at 15±5 minutes, 60±10 minutes, and 120±20 minutes after administration. Panoramic PET-CT scans performed after dosing were acceptable for 1 to 2 subjects in a dose group or each dose group and were required to cover at least one of these time points.
11. Measurement of Radiation Dose: measure the surrounding radiation dose at 4 ± 0.5 hours after administration.
12. PD-L1 Immunohistochemical Examination and Formulate a Plan for Obtaining Target Lesion Specimens (If Performed) : Obtain the PD-L1 immunohistochemical results of the subjects at the study site during the screening period. This experiment determines whether to collect tissue specimens after administration based

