10.4.3 Analysis of the Secondary Endpoints

Immunogenicity evaluation

- Anti-SNA002 antibody: ADA blood samples are collected before administration and on D6 \pm 1d and D28 \pm 2d after administration for the detection of anti-SNA002 antibody in the independent third-party central laboratory.

Evaluation of correlation of expression between imaging and IHC

- The IHC analysis is conducted to the collected tumor tissue samples (tested by the independent third party central laboratory) and the results are compared with those of imaging. Take the immunohistochemistry result as the true values (if only baseline immunohistochemistry result is available, the baseline result is the true value; if both baseline and post administration immunohistochemistry results are available, then post administration results are true values) .Sensitivity [true positive/(true positive + false negative)], specificity [true negative/(true negative + false positive)], positive predictive value [true positive/(true positive + false positive)], and negative predictive value [true negative/(true negative + false negative)] are calculated. Explore the correlation between PET imaging features (such as tumor SUVs, tumor/muscle SUVs) and immunohistochemical results.

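### PET lesion calls need not be recorded before IHC is known, and the committee that reads them also judges PET-IHC agreement, so the exploratory accuracy figures can be biased upward

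*Combined protocol and SAP*

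**What the plan says.** **The committee.** The Study Design row of the Protocol Summary describes it thus: "An independent radiology review committee (IRC), consisting of principal investigator and nuclear medicine physicians, will be established to evaluate all imaging data". Section 6.1.7.2 gives the same membership without the word *independent*: "The Imaging Reviewer Committee consisted of the principal investigator and nuclear medicine physicians".

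**Its access to the reference standard.** Under Dose escalation criteria the Protocol Summary says "IHC results will be reviewed by the IRC" and "The correspondence between the IHC assay results and the PET imaging results will be evaluated by the IRC". For patients who have surgery, the Study Design row adds that "the IRC will observe IHC result of tumor and PET scan".

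**Timing of IHC.** Section 7.3.1 lists PD-L1 IHC among the screening items (D-14 to D-2), and note 12 to Table 4 says "Obtain the PD-L1 immunohistochemical results of the subjects at the study site during the screening period". Section 7.3.3 and note 12 waive a new biopsy if a specimen was taken within two weeks before enrolment and no treatment has followed. Otherwise tissue is collected after dosing, on D2 to D5.

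**Use of IHC.** Section 10.4.3 says "Take the immunohistochemistry result as the true values" and defines sensitivity, specificity, PPV and NPV against it. The post-dose result is used if there is one, and the baseline result if it is the only one.

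The principal investigator also holds the escalation decision: "The dose escalation will be determined by the principal investigator based on both imaging and safety results".

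**The concern.** An accuracy table is informative only if the index test was read without knowledge of the reference. Here one committee holds both, and it also judges their agreement. A reader who knows that a lesion is PD-L1 positive is more likely to call faint uptake positive, and one who knows that it is negative is more likely to dismiss it. Section 10.4.3 gives no PET-positivity cut-off that would limit this discretion.

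At stake are the four accuracy figures and the committee's agreement judgement. They serve the exploratory objectives in section 3 and would be the first human evidence on whether uptake tracks PD-L1 expression. The word *independent* may also lead a reader of the results to assume a separation that the membership does not provide.

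**Working it through.** **1. Is the reference known before the PET read?**

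| Patient group | IHC taken as truth (10.4.3) | Does it exist before the D1 scan? | Rule keeping it from PET readers |
|---|---|---|---|
| Biopsy within 2 weeks before enrolment, untreated, no new tissue | Baseline | Yes | None in the supplied text |
| Tissue taken on D2 to D5 | Post-dose | No | None; PET call not locked |

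In the second group some PET reading must come first, because the Study Design row and section 7.3.3 choose biopsy sites using the PET findings. That reading need not be recorded as the final call, and a screening IHC result may already be known for the same patient. The documents do not say how many patients fall in each group.

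**2. Direction of the bias.** Write TP, FN, TN and FP for the four cells.

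- Re-calling an IHC-positive lesion from PET-negative to PET-positive (FN to TP) raises sensitivity TP/(TP+FN). It raises or leaves unchanged PPV = TP/(TP+FP) and NPV = TN/(TN+FN). Specificity does not move.
- Re-calling an IHC-negative lesion from PET-positive to PET-negative (FP to TN) raises specificity TN/(TN+FP). It raises or leaves unchanged PPV and NPV. Sensitivity does not move.

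All four figures can rise, but specificity rises only through calls changed on IHC-negative lesions.

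**3. Size.** The plan's range reproduces: 4 dose levels × 3 = 12 patients, and 4 × 7 = 28. The documents give no lesion count, IHC-positive fraction or expected sensitivity. Assume one lesion per patient, half IHC-positive, and starting sensitivity near 65%.

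| Patients | IHC-positive | Start | One call changed | Two changed | Shift per call |
|---|---|---|---|---|---|
| 12 | 6 | 4/6 = 66.7% | 5/6 = 83.3% | 6/6 = 100% | 1/6 = 16.7 points |
| 28 | 14 | 9/14 = 64.3% | 10/14 = 71.4% | 11/14 = 78.6% | 1/14 = 7.1 points |

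The shift per call is 1 divided by the number of IHC-positive lesions, so it does not depend on the starting value. The plan allows up to 5 biopsy sites per patient. If several lesions per patient enter the table, each call moves sensitivity less.

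Sampling error is wide in any case: the exact 95% interval is 22.3% to 95.7% for 4/6 and 35.1% to 87.2% for 9/14. The bias differs in kind, because it runs in one direction and the interval does not reflect it.

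**The case against.** - **Weight.** PET-IHC correlation and predictive efficacy are exploratory objectives (section 3) and are not in the endpoint list (section 4.2), although section 10.4.3 files them under secondary endpoints. Section 10.2 sets no hypothesis test. This stands and limits the severity. A descriptive estimate is still biased if the reader knew the answer.
- **Existing safeguards.** Post-dose tissue follows the scan, and a post-dose result replaces the baseline one. Section 7.3.3 sends specimens to an outside central pathology laboratory, although note 12 to Table 4 has IHC performed at the research center; the two need reconciling. Section 10.4.2 bases T/B on SUVmean, and 10.4.3 also correlates SUVs with IHC. The first safeguard is partial because the PET call is not locked. The central laboratory protects the reference, not the PET read. The quantitative measures reduce discretion but do not define the positive/negative call.
- **Documents not supplied.** Imaging procedure is deferred to an SOP (section 9.1), and a formal SAP is to follow (section 10.1). Either could set a blinded read order, so the finding is that none is stated in the supplied text.

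A reader might also infer that the principal investigator personally obtains the screening IHC. Note 12 names only the study site. Nor do the T/B values above 1.5 and at or below 1 in section 6.1.7.2 make 1 to 1.5 a borderline band for PET positivity: they are examples for grading image quality in escalation, and nothing links them to the accuracy table.

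**Conclusion.** The point holds as a correctable weakness in the exploratory accuracy analysis. The committee reads PET, reviews IHC and judges their agreement, includes the principal investigator, and has no stated order of reads. The exposure is direct where baseline IHC is the sole reference and partial where tissue is taken after dosing.

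The effect is about 7 to 17 percentage points of sensitivity per changed call. This assumes one lesion per patient, half of them IHC-positive, across the planned 12 to 28 patients. How many calls would change is unknown, so this is a risk of bias and not an estimate of it.

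A reader might extend the point to the choice of optimal dose, since the committee's judgements feed escalation. The documents do not support that step. The dose-group comparisons rest on image quality, not on calls against IHC. Their readers are not stated to be masked to dose in this open-label trial, and withholding IHC would not change that.

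**What to change.** In the Study Design row of the Protocol Summary and in section 10.4.3, state that:

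1. The nuclear medicine physicians already on the committee record and lock, for each lesion, the SUVs, T/B and a call of positive, negative or not assessable before any screening or post-dose IHC result is released to them.
2. PET-IHC correspondence and all four accuracy figures use only the locked calls.
3. The principal investigator does not make or change those calls.

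Delete *independent* from the Study Design row if the principal investigator remains a reader. If the imaging SOP or the formal SAP already requires a locked, IHC-blind read, cite it instead.

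**Cost.** One dated read form and control over when screening IHC reaches the readers. The number of physicians on the committee is not stated, so the site should confirm that at least one can be kept unaware of IHC until the lock. No additional scans or patients are needed, and the members already named can do the reads. Agreement figures may look less favourable.
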